Answer: Many ICD-9 codes are similar, and the same disease condition may be recorded using slightly different ICD-9 codes during follow-up visits.

21. In this pilot study, a diagnosis is only counted as incident if there were no other diagnoses in the same third level of the tree during the preceding pre-specified X number of days. What are the pros and cons of using the second vs. third vs. fourth level of the hierarchical tree to identify incident diagnoses? How does the definition of incident outcome impact the TreeScan results and the ability to detect alerts?

Answer: A trade-off exists in choosing any tier of the diagnosis tree (e.g., second, third, fourth levels) for defining incident diagnoses. Defining incident events at the second level results in fewer diagnostic events compared to defining them at the third or fourth level, leading to a smaller sample size. Using the fourth level leads to a larger sample size. The additional diagnostic events can either reduce statistical power if they are random noise due to pre-existing conditions recorded during follow-up visits, or they may increase statistical power if they are informative diagnostic events unrelated to pre-existing conditions. Increased power will increase the sensitivity of the method, that is, the ability to detect true adverse reactions. Using the third tier in this pilot was a reasonable approach to start with in view of the trade-offs.

22. Wouldn't the choice of the third level to define incident outcomes cause an increased frequency of second- or fourth-level outcomes in the risk window to be missed?

Answer: The third level is only used to determine if an outcome is incident or not. However the incident diagnosis is defined, all five levels of the tree are evaluated, and the TreeScan method can generate an alert at the first, second, third, fourth, or fifth level of the tree.

23. What happens if there are outcomes that are not more finely differentiated than at the second level of the MLCCS tree? How is such an outcome taken into consideration if incident diagnoses are determined using a higher level?

Answer: We refer to the ICD-9-CM codes that form the basis of the tree that we use as the fifthlevel (i.e., in tree parlance, the leaf level), and hence, that level exists for all outcomes. Aggregation of multiple leaves (i.e., into a branch or trunk of the tree) occurs at the first through fourth levels. Sometimes, the MLCCS tree ends at the second or third levels. In such cases, we have artificially filled in the tree up to the finest level of aggregation, i.e. the fourth level. For example, ICD-9 code 729.5, "pain in soft tissues of the limb," corresponds to a second level outcome on the tree, 13.08, in which the first level 13 is "diseases of the musculoskeletal system and connective tissue" and the second level 08 is "other connective tissue disease." There is no finer MLCCS differentiation of this outcome, but additional levels were created for it by adding zeroes — the third level is 13.08.00 and the fourth level is 13.08.00.00.

IMPLEMENTATION AND TREESCAN PARAMETER SELECTION

24. Why was an observation period of Days 1-56 chosen, and why will only risk windows that are at most 28 days long (and that start 1-28 days after vaccination and end 2-42 days after vaccination) be considered?

Answer: In theory, clusters of any duration can be evaluated. In practice, a self-control design is most suited to detect outcomes that happen during a well-defined risk period after vaccination, so our early efforts are focused on early-onset outcomes. In this pilot of the TreeScan method, we chose not to use an observation period of longer than Days 1-56 after vaccination, because Gardasil Dose 2 is commonly given approximately 2 months after Dose 1, and we wished to avoid having control time for Dose 1 overlap with the risk period for Dose 2. With an observation period of 56 days, if we were to look for and detect risk intervals that were longer than 28 days, it would more accurately reflect a *decreased* risk in the few days *outside* the interval rather than an *increased* risk *inside* the interval. Moreover, it is desirable, for reasons of statistical power, to use an observation period of twice the length of the maximum cluster length one is looking for. So clusters lasting more than 28 days could be assessed, but in that case we would want to use a longer follow-up period.

25. How does TreeScan handle multiple doses of a vaccine or other exposure?

Answer: Currently, due to the nature of the data extraction program (as opposed to the TreeScan[™] software), only first doses can be identified. The ability to identify and evaluate multiple doses will be developed in future enhancements to the data extraction program.

26. What would the consequences be, for the TreeScan analysis with a 56-day follow-up period, of Gardasil Dose 2 being administered within 56 days of Dose 1?

Answer: The recommended spacing of Gardasil doses has been 0, 1-2, and 6 months. Dose 2 is sometimes given within 56 days of Dose 1. If this were not an unusual occurrence, then a true association between (the unascertained) Dose 2 and one or more outcomes (concentrated, for example, during the first 2 weeks after (the unascertained) Dose 2 and often falling during Days 43-

56 after Dose 1) would lead to an attenuation of the apparent risk of these outcomes from Dose 1. However, most Dose 2's are given more than 56 days after Dose 1, so we would not expect such attenuation to be a major problem.

27. Instead of using the same rules to define incident outcomes, set the observation period, etc., for all outcomes, wouldn't it make more sense to tailor the rules to the various outcomes, some of which would have more acute and/or immediate onsets than others?

Answer: Customization of the rules for specific outcomes is not feasible with a method of this kind, where there are thousands of different outcomes being assessed. This is an early-warning, alert-detection system. Definitions of incident outcomes, risk intervals, and other parameters can and should be customized in subsequent alert investigations.

LOOKING AHEAD

28. Can TreeScan be used to identify statistically protective effects as well as excess risks? If so, how?

Answer: Currently, this cannot be done when using the Poisson or tree-temporal versions of the TreeScan software, because a one-sided statistical test is implemented. A future version of TreeScan will be able to do two-sided tests. Theoretically, when using the TreeScan Bernoulli option for a self-control analysis, it is possible to do a one-sided test for a protective effect by simply redefining the risk interval as the control interval and the control interval as the "protective interval." However, the evaluation of effectiveness using TreeScan is more complex and is not a current goal for Sentinel.

29. What kind of investigations will be undertaken if and when unexpected safety alerts arise from TreeScan analysis, and how will decisions about those investigations be made?

Answer: A manuscript is in development that will present the planned approach to investigating alerts from TreeScan. In general, the approach is as follows: We will first identify whether alerts correspond to a known or expected association, such as those noted in the product label. Then, of the remaining alerts, we will consider the potential biases that might have been operating and the strength of the bias needed to generate a false alert. We may perform additional alert follow-up under the guidance of the Food and Drug Administration.

30. If TreeScan alerts arise, how can we be sure that the alert is not related to one particular Data Partner?

Answer: Any alert investigation will consider the possibility that a TreeScan alert is Data Partner-specific and will include stratification of data by Data Partner.

31. Can TreeScan be used to monitor the safety of drugs as well as vaccines?

Answer: TreeScan has been applied to pharmaceutical drugs. When the method was applied to two antifungal drugs and two diabetes drugs, known adverse reactions were found.^{1,5} However,

TreeScan is still being piloted and is not in widespread use for either drug or vaccine safety monitoring.

XVII. REFERENCES

- 4) Kulldorff M, et al. A Tree-Temporal Scan Statistic for Drug and Vaccine Safety Data Mining. Manuscript, 2014.

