The method formally adjusts for the multiple testing generated by the many groupings of outcomes and many potential risk windows that are evaluated in a single analysis for a specific exposure. The secondary analyses represent additional multiple testing, which is not formally adjusted for. In the secondary analyses, we will adjust for this additional multiple testing informally by using an alpha level of 0.01 to reject the null hypothesis.

IV. UNCONDITIONAL TREE-TEMPORAL SCAN STATISTIC

With the tree-temporal scan statistic, we are performing multiple temporal scan statistics, one for each of the many overlapping branches of the tree, adjusting for the multiple testing stemming both from the many branches and from the many time intervals evaluated. Each time interval is evaluated on each of the branches, so if there are, for example, 1000 nodes on the tree and 2002 potential time intervals, there would be 2,002,000 potential clusters to evaluate and for which we would need to adjust for multiple testing. If these were 2 million independent tests with non-overlapping data, there would be a huge loss in power when adjusting for all the multiple testing. With scan statistics, such a large loss in

Mini-Sentinel CBER/Prism Methods Protocol

power does not happen, since many of the 2 million potential clusters are highly overlapping with each other. Hence, the penalty for adjusting for the multiple testing is more modest.

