Considering the thousands of overlapping disease outcome definitions evaluated, adjustment for multiple testing is critical. This is accomplished through the simulation component of the method. The likelihood ratio test statistic from the most likely cut in the real dataset is compared with the likelihood ratio test statistics from the most likely cuts in each of, say, 999 random datasets, and we note its rank. For example, if it has the fifth highest test statistic, its rank is 5. Note that the most likely cut will be on a different branch in the different datasets, so we are not comparing the likelihood ratios for the same cut, but rather, comparing the maxima of the likelihood ratios obtained over all possible cuts. Since the random datasets were all generated under the null hypothesis, if the null hypothesis is true in the real dataset, then the test statistics come from exactly the same probability distribution. This means that, if the null hypothesis is true, the rank test statistic from the real dataset will range uniformly from 1 to 1000, and the probability of having a rank in the top 5% is exactly 5%. If the test statistic from the real dataset is in the top 5%, we will reject the null hypothesis; we have a 5% probability of falsely rejecting the null.

The tree-temporal scan statistic conditions the analysis on the number of cases observed in each node of the tree. This means that, unlike the standard tree-based scan statistic, there is no probability distribution to model the number of cases in each node, but rather, it is deterministic. What is probabilistic is the timing of each case, which under the null hypothesis is assumed to be uniform across the follow-up period. Under the alternative hypothesis, there is at least one branch for which there is a temporal cluster of cases during some time interval.

With the tree-temporal scan statistic and under the null hypothesis, any outcome is equally likely to occur on any of the days following the initial drug/vaccine exposure. For each tree node and time interval, we calculate the log likelihood ratio (LLR) test statistic:

$$LLR = \ln \frac{\left(\frac{c}{n}\right)^{c} \left(\frac{n-c}{n}\right)^{n-c}}{\left(\frac{w}{T}\right)^{c} \left(\frac{T-w}{T}\right)^{n-c}} I(c/n > w/T)$$

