likely cluster is statistically significant, after adjusting for the multiple testing inherent in the many nodeinterval combinations considered, Monte Carlo hypothesis testing is used. This is done by generating, say, 999 random replicates of the data. In each random data set, each node has exactly the same number of cases as the real data set, but the post-exposure timing of those cases varies, with each one generated from a uniform distribution independent of each other case. For each random data set, generated under the null hypothesis, we find the most likely cluster in the same way as we did for the real data set, and we note the maximum LLR of that data set. Note that the node and time interval for the most likely cluster will typically be different in each of the random data sets and also different from the real data. If the null hypothesis is true, then the maximum LLR from the real data set has a 5% chance of being among the 50 highest maximum LLRs from the real and random data sets, so if that is the case, we can reject the null hypothesis at the alpha=0.05 level. If R is the rank of the maximum LLR from the real data set, so that there are exactly R-1 random data sets with a higher maximum, the Monte Carlo based p-value is R/(S+1), where S is the number random data sets used. Adjustment for multiple testing is assured since we are comparing the maximum from the real data set with the maxima from the random data sets.

The tree-temporal scan statistic can be applied with various analysis parameter settings. We will only evaluate outcomes occurring 1 to 56 days after vaccination. The day of vaccination is not included since (i) a well care visit at which vaccines are given could generate diagnosis codes (outcomes) unrelated to vaccination, such as problems found during an eye examination, or (ii) vaccines may be given during a health care visit that happened due to a different health concern. In other words, the null hypothesis should be that all diagnosis codes (outcomes) occur with equal probability on each day, and that is clearly not the case for the day of vaccination.

V. POWER EVALUATION

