tree. For example, since myocardial infarction (07.02.03) is often preceded by chest pain (07.02.05) a few days before, a patient may be counted twice at the 07 and 07.02 level analyses, and the tree based scan statistic will erroneously ignore the dependence of these events. While we have not seen any evidence of problems caused by this dependence in previous work, the possibility of such a problem should be kept in mind when evaluating statistical alerts at the two highest levels of the tree.

To capture the most serious types of outcomes, we are using outcomes recorded at emergency department visits and inpatient hospital stays. Outcomes in outpatient settings will be excluded. This could be either an advantage or a disadvantage. A potential disadvantage is reduced power to detect adverse reactions that are primarily treated in an outpatient setting.

While the self-control tree-based scan statistic automatically adjusts for all non-time varying confounders, it does not adjust for time-varying confounders. Examples of potential time-varying confounders are:

- Seasonality: HPV vaccine uptake has a demonstrated pattern of seasonality, with the greatest uptake occurring in August prior to the start of the school year. Thus, seasonality is a potential source of confounding in the case of outcomes that also are seasonal in nature. This bias could go in either direction.
- *Concomitant exposures:* By design, HPV vaccine is recommended to be administered as part of the "adolescent" set of vaccines at 11-12 years old. This set also includes meningococcal and tetanus-diphtheria-acellular pertussis vaccines. Given the frequent co-administration of these vaccines, a statistical alert that appears in HPV safety monitoring may in fact be associated with one or more concomitant vaccines instead.
- Concomitant routine screening: HPV vaccine administration is likely to occur with routine screenings for participation in school sports and recommended screenings for sexually transmitted diseases and mental health conditions among portions of this population. The medical evaluation (follow-up) that results from these routine screenings may occur during the surveillance period and appear to be attributable to the vaccine. For example, some girls may start oral contraceptive use at the same time as they get the HPV vaccine, and an adverse reaction to the oral contraceptive could then show up as a statistical alert after HPV vaccination.

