TREESCAN EXECUTION							
Scan the tree	Scan the tree to find most likely and secondary cuts/clusters.			rs.	Perform the temporal scan on each potential cut on the tree, to find most likely and secondary clusters.		
Random Monte Carlo data sets	Generated from expected counts, using Poisson distribution. Random data sets may have more or less total AEs than the real data.	Conditioned on total number of AEs , so that each random data set has exactly the same number of total AEs as the real data set. The random number of AEs for a particular ICD9 code is binomially distributed as Bin(n,p), where n is the total number of AEs and p is the expected count in the leaf divided by the total expected count summed over the whole tree.	Generated using the specified risk interval probability. For each ICD9 code, the sum of the AEs in the risk and control intervals will be the same in each random data set and the real data set. The total number of AEs in the risk interval, summed over all ICD9 codes, may be different in the random and real data sets.	For each ICD9 code, the sum of the AEs in the risk and control intervals will be the same in each random data set and the real data set. The total number of AEs in the risk interval summed over all ICD9 codes, C, is the same in each random data set and the real data. Randomization is conducted by randomly picking C of the AEs to be assigned to the risk interval.	For each ICD9 code, the sum of the AEs taken over all days will be the same in each random data set and the real data set. Independently of every other AE, an AE is assigned to a day using a uniform distribution where each day in the follow-up period is equally likely to be chosen.	For each ICD9 code, the sum of the AEs taken over all days will be the same in each random data set and the real data set. For each day, the total number of AEs on day X, summed over all ICD9 codes, is the same in each random data set and the real data. Randomization is conducted by randomly permuting the days and the ICD9 code pairings, keeping the marginals fixed.	
INTERPRETATION							
Self-controlled		No		Ye	s		
Pre-defined risk interval	Yes No						
Adjusts for multiple testing Adjusts for temporal variation common to all ICD9 codes	No	Yes	No	Yes	No	Yes	

XV. APPENDIX 2: EXAMPLES OF FICTIONAL PATIENTS

Fictional Patient A 18 year old with depression and pelvic inflammatory disease

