Answer: It is unlikely, since the method adjusts for the multiple testing inherent in the thousands of outcomes and groups of related outcomes that are evaluated. Suppose you use an alpha level of 0.05, declaring an alert when p≤0.05. If you perform 100 TreeScan analyses, the expected number of TreeScan analyses without any alerts due to chance is 95. If the null hypothesis is true, the expected number of TreeScan analyses without any alerts at all is 95. In other words, in the long run, 5 percent of your TreeScan analyses will contain a false positive alert that is due to chance. If this is considered too high, you can instead use an alpha level of 0.01. Then, in the long run, only 1

percent of your TreeScan analyses will contain a false positive alert that is due to chance.

9. A higher frequency of healthcare visits and diagnosis codes has been observed in the first two weeks after vaccination than subsequently, usually due to workup of conditions that were present at the time of vaccination and diagnosed shortly thereafter. Wouldn't you expect false TreeScan alerts to arise due to this phenomenon?

Answer: It depends on the type of TreeScan analysis. It is easy to test whether this phenomenon is present in a particular dataset by comparing the total outcomes in different periods after vaccination. Whether it is present depends on the age group and the vaccine exposure being studied. When present, it can bias the unconditional self-control and the unconditional tree-temporal scan statistics. On the other hand, the *conditional* versions are explicitly designed to adjust for this type of bias, although they will only adjust for the general phenomenon across all outcomes, not for an exceptionally strong time bias for a specific outcome. The latter must be dealt with either using an adjusted Poisson TreeScan analysis or in the alert investigation stage.

10. Could bias enter a TreeScan analysis as a result of differences in recommendations for use of the product (including the timing of rollout) among different demographic subgroups, such as males vs. females?

Answer: In using a self-controlled version of TreeScan, there would be no bias introduced by differential use of the product by different subgroups, nor by differences in the timing of rollout to different subgroups.

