Answer: Relying on electronic healthcare databases has key advantages, including the efficient capture of the healthcare experiences of a large patient population for analysis. However, there are fundamental limitations to using administrative claims data for vaccine safety surveillance that will not be automatically overcome with TreeScan (no matter what its inherent strengths), such as variability in coding practices across the full range of outcomes evaluated. For this reason, all TreeScan alerts must be evaluated with coding variability in mind.

One of TreeScan's strengths is that an investigator is not required to pre-specify how a clinical concept will be coded in administrative data. For example, different physicians could code an outcome slightly differently, for example, coding a febrile seizure as

- convulsions (780.3), or
- febrile convulsions NOS (780.31), or
- complex febrile convulsions (780.32).

The tree structure can detect an alert by combining related diagnoses at more coarsely-aggregated levels of the tree even when a singular diagnosis does not have a large enough sample size to generate an alert independently.

Mini-Sentinel CBER/ PRISM Methods Protocol - 22 -

19. What is the purpose of defining and using incident diagnoses, rather than using all recorded diagnoses?

Answer: A diagnosis is an incident diagnosis if there is no prior diagnosis of the same or similar kind in the prior "X" days. The primary goal of the incident diagnosis definition is to identify only newonset events and distinguish them from ongoing conditions that existed before vaccination. By removing such ongoing conditions, the signal-to-noise ratio increases, which in turn increases statistical power. A second reason for using only incident diagnoses is to ensure that a person can only contribute one event during the post-exposure follow-up period in the same user-defined level of the tree. This is further accomplished by ensuring that the number of days used in the incident diagnosis definition is longer than the post-exposure follow-up time. Together, these operational characteristics help to ensure the independence assumptions that underlie the TreeScan probability models.

20. Why is an incident diagnosis defined based on the second, third, or fourth level of the diagnosis tree rather than on ICD-9 codes?

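### The 5% false-alert rate is stated without the independence condition, which the event-counting rule breaks at the two broadest tree levels

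*Protocol*

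**What the plan says.** **Error rate.** Section IV says that under the null "the probability of having a rank in the top 5% is exactly 5" per cent, and that for a maximum among the top 50 of the real and random data sets "we can reject the null hypothesis at the alpha=0.05 level". Appendix 3, Q5 repeats the claim of exactness. Q8 restates it as a frequency: "in the long run, 5 percent of your TreeScan analyses will contain a false positive alert that is due to chance". Secondary analyses adjust informally by "using an alpha level of 0.01 to reject the null hypothesis" (Section III).

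**Randomisation.** In the unconditional version each case gets its own day, independently of every other case (Section IV). In the conditional version, which is the primary analysis, Appendix 1 says: "Randomization is conducted by randomly permuting the days and the ICD9 code pairings, keeping the marginals fixed".

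**Counting.** Section IX allows several incident diagnoses per member if they are on different third-level branches. Appendix 2 reduces codes from one visit to a single code only within a third-level branch. Appendix 3, Q22 confirms that all five levels are scanned.

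**Disclosure.** Section XIII gives chest pain followed a few days later by myocardial infarction as a case counted twice at levels 1 and 2. It says that "the tree based scan statistic will erroneously ignore the dependence of these events", that earlier work showed no sign of trouble, and that alerts at the two highest levels should be read with this in mind. Appendix 3, Q19 says of the incident definition and look-back: "Together, these operational characteristics help to ensure the independence assumptions that underlie the TreeScan probability models".

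**Data.** Section XI.A has the sites supply a patient index. The TreeScan file in Section XI.B holds only code, count and day.

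**The concern.** The Monte Carlo reference distribution is right only if the rows in a node are independent in time. When one patient puts two rows on the same or nearby days into one node, the real counts vary more than the row-by-row randomisation allows. The real maximum then ranks too high too often. The incident rule prevents this within a third-level branch and below, but not at levels 1 and 2.

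What is at stake is the p-value of the primary analysis and the three secondary ones. The surplus false alerts would fall on broad nodes, which are the hardest to interpret, and no planned analysis separates them from real or confounded ones.

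**Working it through.** **1. The plan's own figure.** With 999 replicates and rejection at rank 50 or better, 50/(999 + 1) = 0.05. The rank arithmetic is right.

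**2. Windows scanned (Section X).** Starts on days 1-15 allow 27 lengths each: 15 × 27 = 405. Starts on days 16-28 allow 26 down to 14: 13 × 20 = 260. The total is 665.

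**3. Why the spread is too narrow.** Suppose a node is fed by V visits and a share f of them add a second same-day row. Let q be the null probability of the window.
- Rows: V(1 + f). Variance under row-by-row randomisation: V(1 + f)q(1 − q).
- Actual variance: single visits contribute q(1 − q) and double visits 4q(1 − q), which gives V(1 + 3f)q(1 − q).
- Ratio: (1 + 3f)/(1 + f). It exceeds 1 for any f above 0.

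Fixing the day totals does not keep a patient's rows together, so the conditional version is affected too. The test looks for excess only, "because a one-sided statistical test is implemented", so the extra spread goes straight into false alerts.

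**4. Simulated size at nominal 5%.** The Section IV likelihood ratio was maximised over 665 windows and all nodes. For the conditional version w/T was replaced by the share of all events falling in the window. That form is an assumption, since the protocol prints only the unconditional formula. Other assumptions are 3,000 or 15,000 visits, synthetic trees, and f from 0 to 30% with the second diagnosis on another third-level branch of the same second-level node. The simple tree has levels 1-3 (2,000 replicates per scenario). The full tree adds a leaf level (15 × 7 × 5 × 3 branching; 800 replicates for f = 0 and 5%, 600 otherwise).

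| f | Variance ratio | Simple tree, both versions, 3,000 and 15,000 visits | Full tree, conditional, 15,000 visits | Share of full-tree false alerts at levels 1-2 | Full tree, whole visits permuted |
|---|---|---|---|---|---|
| 0 | 1.00 | 4.7-5.2% | 5.2% | 5% | 3.9% |
| 5% | 1.15/1.05 = 1.10 | 7.0-9.5% | 6.5% | 23% | 5.2% |
| 10% | 1.30/1.10 = 1.18 | 9.1-11.8% | 7.3% | 30% | 4.0% |
| 20% | 1.60/1.20 = 1.33 | 22.5-26.1% | 16.0% | 66% | 6.5% |
| 30% | 1.90/1.30 = 1.46 | 35.7-37.7% | 19.3% | 78% | 4.0% |

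With independent diagnoses the 5% is reproduced.

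**5. Precision at the low end (full tree).** For f = 5% the standard error is √(0.065 × 0.935/800) = 0.9 points. For f = 10% it is √(0.073 × 0.927/600) = 1.1 points. The critical value was itself estimated from as many null data sets, which adds error. These two results are hard to tell from 5%.

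**6. Other settings.**
- Second diagnosis 0-3 days later, f = 20%, simple tree: 11.6-16.8%.
- Nominal 1%, same day, f = 20%, simple tree: 7.1-10.3%.
- Larger tree (18/100/300 nodes and 3,000 leaves, about 45,000 events, conditional, 1,000 data sets per scenario), with first-level variance inflation of 1.26, 1.38, 1.61 and 1.90: 6.9%, 6.8%, 9.0% and 21.9% (standard error about 0.8-1.3 points).

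**The case against.** The strongest reply is that the protocol discloses the dependence, places it at the right levels and says how to read such alerts. This is a methods pilot, every alert is assessed for bias (Section XII), and no causal conclusion rests on an alert. That limits the harm. It neither corrects the p-value nor qualifies the 5%. The reassurance from earlier work cannot cover the primary analysis, because Section I describes the conditional tree-temporal statistic as not yet developed.

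Four stronger readings are tempting, and the document does not support them.

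- *Appendix 2 shows tied events.* Fictional Patient A has nine post-vaccination codes, three of them from the outpatient visit, so six belong to the second emergency visit. Only one of those is retained. The other patient's two retained codes come from different visits. Neither example leaves two same-day events, and nothing says that same-day pairs are commoner than lagged ones.
- *The exactness claim is false as algebra.* It is conditional on the null, and the null as simulated includes independence. The fault is that the planned data need not meet that condition and the sentence does not say so.
- *The dependence spoils the comparison of versions.* It affects both, and no rule makes the count of level-1 or level-2 alerts the criterion for choosing between them.
- *The plan cannot correct this.* The sites supply a patient index. It is simply not carried into the analysis file.

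The point about size also stands: visit counts, tree shapes and co-coding rates above are all assumed, and the 183-day look-back in any setting removes some multiple coding.

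**Conclusion.** The concern holds in this limited form. Row-by-row randomisation combined with a third-level counting rule makes the adjusted p-values anti-conservative in both versions, with the excess at levels 1 and 2. The direction follows from the protocol's own rules, provided some patients have diagnoses on the same or nearby days under one such node. The protocol's chest-pain example is of that kind.

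The size cannot be fixed from the document. On full trees it runs from about 6.5-7% at low co-coding to about 20% at high co-coding. The simple tree gives larger figures, but it omits the finer nodes that make up much of the real scan. None of these is an estimate for the planned data. Because alerts are screened and not taken as causal, this is a change that should be made rather than a fault that invalidates the analysis.

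**What to change.** 1. **Check broad alerts on reduced data.** Keep the patient index through data preparation. For any level-2 alert, re-run the same scan at the same alpha on data holding one event per patient per second-level branch. For any level-1 alert, use one event per patient per first-level branch. Leave the third-level look-back rule unchanged. Fix in advance which event is kept, for example the earliest. A seeded random choice is an alternative, since always keeping the earliest tilts the reduced data slightly toward early days. Report whether the alert persists, and flag any that does not as possibly due to within-patient dependence. This covers both same-day and lagged pairs.
2. **Optional, in the code being written.** Permute whole patient-day blocks among blocks of equal size (conditional version), or draw one day per block (unconditional version). Permuting whole visits brought the simulated rate back to 3.9-6.5%. It corrects same-day ties only, so it would leave the chest-pain-then-infarction example untouched and does not replace item 1.
3. **Wording.** In Section IV and in Appendix 3, Q5 and Q8, say that the 5% holds only if events are independent, with a cross-reference to Section XIII.

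**Cost.** One extra run that is not now planned: Section IX only tabulates outcome counts under second-, third- and fourth-level definitions. Some level-1 or level-2 alerts will be flagged or lost. The wording change costs nothing.
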